# 6.11 Dosing of Standard of Care

The number and percentage of subjects using remdesivir or dexamethasone (or both) will be summarized by treatment group.

All standard of care information will be listed.

# **6.12 Efficacy Analyses**

All statistical tests will be performed using a two-tailed 5% overall significance level, unless otherwise stated. All comparisons between treatments will be reported with 95% confidence intervals for the difference.

# 6.12.1 Primary Endpoint

QMD Ref: Worldwide-TMP-ST-005-7.0 Effective: 12Aug2019 Governing QMD: Worldwide-SOP-ST-		
Confidentiality Statement		
This document is the property of Worldwide Clinical Trials Inc. and may not be duplicated, copied, altered or removed from company without prior approval from Worldwide Quality Assurance or in compliance with Worldwide Standard Operating Procedures.		

REF: Worldwide-TMP-QA-001f-1.3

Worldwide Clinical Trials Controlled Quality Management Document		
WORLDWIDE CLINICAL TRIALS	Sponsor:	Veru Inc.
	Protocol Number:	V0211901
STATISTICAL ANALYSIS PLAN. PHASE 2-3-4		

The primary endpoint for the study is the proportion of subjects that are alive without respiratory failure at Day 29. Respiratory failure is defined as endotracheal intubation and mechanical ventilation, extracorporeal membrane oxygenation, high-flow nasal cannula oxygen delivery, noninvasive positive pressure ventilation, clinical diagnosis of respiratory failure with initiation of none of these measures only when clinical decision making is driven solely by resource limitation.

This analysis will compare the percentage of subjects that are alive without respiratory failure on Day 29 (responder).

Responders are subjects who have Grade 0-4 on the WHO Ordinal Scale for Clinical Improvement on Day 29. If subject was discharged from the hospital prior to Day 29 and WHO Ordinal Scale for Clinical Improvement is not collected at Day 29 then the last available observation before or at the time of discharge will be carried forward.

Non-responders are subjects who died before Day 29 or has Grade 5, 6, 7, or 8 on the WHO Ordinal Scale for Clinical Improvement on Day 29.

The number and percentage of responders will be summarized by treatment group. Responders will be analyzed using a logistic regression model. This model will include treatment as a factor, and study site, remdesivir use (No/Yes), dexamethasone use (No/Yes) and WHO Ordinal Scale for Clinical Improvement at baseline as a covariates. Odds ratios, standard errors, 95% confidence intervals and p-values for the treatment difference will be presented.

The primary analysis will be performed on the ITT population. A sensitivity analysis will be performed repeating the analysis on the EE population.

Example SAS code for the analysis is as follows:

Responder rates and differences between treatment groups in responder rates will be calculated as sensitivity analysis for primary endpoint. Wald method will be used for 95% confidence intervals and testing of treatment differences.

QMD Ref: Worldwide-TMP-ST-005-7.0 Effective: 12Aug2019	Governing QMD: Worldwide-SOP-ST-001	
Confidentiality Statement		
This document is the property of Worldwide Clinical Trials Inc. and may not be duplicated, copied, altered or removed from company without		
prior approval from Worldwide Quality Assurance or in compliance with Worldwide Standard Operating Procedures.		

REF: Worldwide-TMP-QA-001f-1.3

Worldwide Clinical Trials Controlled Quality Management Document		
WORLDWIDE CLINICAL TRIALS	Sponsor:	Veru Inc.
	Protocol Number:	V0211901
STATISTICAL ANALYSIS PLAN, PHASE 2-3-4		

Example SAS code for the analysis is as follows:

```
proc freq data=XXX order=internal;
tables avisitn*trt01pn*avalc / riskdiff(column=2 equal var=null cl=wald);
exact riskdiff barnard(column=2);
ods output riskdiffcol2=riskdiff1 pdiffcls=waldci1 pdifftest=waldtest1
barnardstest=barnard1;
run;
```

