8.2 Enrollment

Enrollment should be done after the subject has completed the screening assessments and after it has been determined that the subject meets all the inclusion and exclusion criteria.

Subject will be randomized into one of two treatment groups.

8.3 Day 1

The Day 1 visit assessments will serve as the baseline assessments.

- 1. The medical history should be reviewed and updated to include any changes occurring since the screening visit. This will include the following:
 - a. Number of days from onset of COVID-19 symptoms to Day 1

- b. Specific reason for hospitalization
- 2. Assessment of eligibility
- 3. Vital signs (temperature/pulse/supine, if possible, blood pressure)
- 4. SpO_2
- 5. Physical examination (including weight)
- 6. Chest X-ray or Computed Tomography (CT) scan
- 7. Clinical Laboratory Tests
 - a. Hematology (Appendix A)
 - b. Serum chemistry (Appendix A)
 - c. Urinalysis
- 8. Record the usage of any concomitant medications and ongoing treatments.
- 9. Adverse events (ongoing on Day 1)
- 10. First dose of study drug
- 11. Temperature and SpO₂ every 12 hours after dosing

8.4 Day 2 through Day 21

The following assessments will be conducted on each of Day 2 to Day 21

- 1. Temperature and SpO₂ every 12 hours
- 2. Vital signs (temperature/pulse/supine, if possible, blood pressure)
- 3. Record the usage of any concomitant medications and ongoing treatments. This should include the following:
 - a. Documentation of the standard of care
 - b. The clinical rationale for initiation of mechanical ventilation, if necessary
 - c. Documentation of supportive measures for ARDS (e.g., proning, paralytics, etc.)
 - d. Care decisions that are based on limitations of resources at the clinical site
- 4. Adverse events
- 5. Dose study drug
- 6. At the time of discharge from the hospital, patients should be advised to use refrain from prolonged exposure to the sun or use at least SPF 50 on all exposed skin and protective clothing during prolonged sun exposure until the Day 60 adverse event assessment.

8.5 Day 3, Day 9, and Day 15

The following additional assessment will be conducted on Days 3, Day 9 and 15:

- 1. Serum Chemistry (Appendix A)
- 2. Hematology (Appendix A)
- 3. Assessment of primary and secondary endpoints (Day 15 only)
- 4. Physical examination (including weight) (Day 15 only)
- 5. 12 lead ECG (single) (Day 15 only)
- 6. Pregnancy test (Day 15 only)

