# WORLDWIDE STATISTICAL ANALYSIS PLAN. PHASE 2-3-4

The primary endpoint for the study is the proportion of subjects that are alive without respiratory failure at Day 29. Respiratory failure is defined as endotracheal intubation and mechanical ventilation, extracorporeal membrane oxygenation, high-flow nasal cannula oxygen delivery, noninvasive positive pressure ventilation, clinical diagnosis of respiratory failure with initiation of none of these measures only when clinical decision making is driven solely by resource limitation.

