# 3.2 Secondary Endpoints

The secondary endpoints on this study are:

1. WHO Ordinal Scale for Clinical Improvement (8-point ordinal scale):

Patient State	Descriptor	Score
Uninfected	No clinical or virological evidence of infection	0
Ambulatory	No limitation of activities	1
	Limitation of activities	2
Hospitalized, Mild disease	Hospitalized, no oxygen therapy	3
	Oxygen by mask or nasal prongs	4
Hospitalized, Severe disease	Non-invasive ventilation or high- flow oxygen	5
	Intubation and mechanical ventilation	6
	Ventilation + additional organ support – pressors, Renal Replacement Therapy (RRT), Extracorporeal Membrane Oxygenation (ECMO)	7
Death	Death	8

2. Proportion of subjects that are Grade 5, 6, 7, or 8 on the WHO Ordinal Scale for Clinical Improvement at Day 15

QMD Ref: Worldwide-TMP-ST-005-7.0 Effective: 12Aug2019 Governing QMD: Worldwide-SOP-S		
Confidentiality Statement		
This document is the property of Worldwide Clinical Trials Inc. and may not be duplicated, copied, altered or removed from company without		
prior approval from Worldwide Quality Assurance or in compliance with Worldwide Standard Operating Procedures.		

Worldwide Clinical Trials Controlled Quality Management Document			
WORLDWIDE	Sponsor:	Veru Inc.	
CLINICAL TRIALS	Protocol Number:	V0211901	
STATISTICAL ANALYSIS PLAN, PHASE 2-3-4			

- 3. Proportion of subjects that are Grade 5, 6, 7, or 8 on the WHO Ordinal Scale for Clinical Improvement at Day 22
- 4. Proportion of subjects that are Grade 5, 6, 7, or 8 on the WHO Ordinal Scale for Clinical Improvement at Day 29
- 5. Change in mean WHO Ordinal Scale for Clinical Improvement at Day 15
- 6. Change in mean WHO Ordinal Scale for Clinical Improvement at Day 22
- 7. Change in mean WHO Ordinal Scale for Clinical Improvement at Day 29
- 8. Proportion of subjects with normalization of fever and oxygen saturation through Day 15. This will be a composite of fever normalization maintained for at least 24 hours AND peripheral capillary oxygen saturation (SpO2) >94% sustained for 24 hours.
- 9. Proportion of subjects with normalization of fever and oxygen saturation through Day 22. This will be a composite of fever normalization maintained for at least 24 hours AND peripheral capillary oxygen saturation (SpO2) >94% sustained for 24 hours.

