#### Example SAS code for the analysis is as follows:

# 6.12.2.2 Proportion of subjects that are Grade 5, 6, 7, or 8 on the WHO Ordinal Scale for Clinical Improvement at Day 15, Day 22, and Day 29

As the primary endpoint will be using WHO scale to define responders/non-responders this analysis specified in the protocol would be corresponding to the primary endpoint. Primary endpoint analysis table will include Days 15, 22 and 29 which makes this analysis redundant. Therefore this secondary endpoint will be dropped out.

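### The SAP's Day 29 responder rule omits the resource-limitation part of its own respiratory-failure definition, so a subject in such failure without a device would count as a success

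*SAP*

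**What the plan says.** SAP 6.12.1 opens with the endpoint: "The primary endpoint for the study is the proportion of subjects that are alive without respiratory failure at Day 29". It then defines respiratory failure as intubation with mechanical ventilation, ECMO, high-flow nasal oxygen or noninvasive positive pressure ventilation, and adds one further route: "clinical diagnosis of respiratory failure with initiation of none of these measures only when clinical decision making is driven solely by resource limitation". SAP 3.1 and Protocol 5.3.1 and 9.3.1 carry the same definition.

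The rule to be programmed follows in the same SAP section. On one side, "Responders are subjects who have Grade 0-4 on the WHO Ordinal Scale for Clinical Improvement on Day 29". On the other, "Non-responders are subjects who died before Day 29 or has Grade 5, 6, 7, or 8 on the WHO Ordinal Scale for Clinical Improvement on" (the quote stops just before the visit, which is the same one). Neither sentence mentions a clinical diagnosis or a shortage of resources.

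SAP 6.12.2.6 applies the same analysis at Days 15 and 22. SAP 6.12.2.2 drops the protocol's separate Grade 5 to 8 endpoint because the primary-endpoint table will cover those days, "which makes this analysis redundant". SAP section 9 lists that deletion as a change to the protocol analysis. It does not list any narrowing of the primary endpoint.

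Protocol 8.4 asks sites to document, on Days 2 to 21, "Care decisions that are based on limitations of resources at the clinical site". No derivation in the SAP uses that record.

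**The concern.** The definition and the derivation disagree about one kind of subject, and the derivation is what will be analysed. The definition has a route to failure that needs no device. The WHO scale, as printed in SAP 3.2, cannot see that route, because its grades for living inpatients describe the support received. Without a further condition, a subject who meets the definition of failure by that route is reported as a success.

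The trial plans about 20 subjects per arm, so a single classification carries weight. The clause is repeated wherever either document defines the endpoint, and the protocol asks for supporting documentation. It should therefore not disappear from the analysis without being declared.

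**Working it through.** **1. Definition against rule.** The inputs are the definition and rule in SAP 6.12.1 and the scale in SAP 3.2.

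| State at the visit | WHO grade | Stated definition | SAP rule |
|---|---|---|---|
| Intubated and ventilated | 6, or 7 with added organ support | Failure | Non-responder |
| ECMO | 7 | Failure | Non-responder |
| High-flow oxygen or noninvasive ventilation | 5 | Failure | Non-responder |
| Died before the visit | 8 | Failure | Non-responder |
| Alive inpatient, failure diagnosed, no listed measure started solely for lack of resources | 3 or 4 | Failure | **Responder** |

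Grade 3 is "Hospitalized, no oxygen therapy" and Grade 4 is "Oxygen by mask or nasal prongs". Grade 5 requires noninvasive ventilation or high-flow oxygen to be in use. The first four rows agree and only the last row conflicts.

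**2. Check against the SAP's own reasoning.** The listed devices fall in Grades 5 to 7 and death is Grade 8. The last row is therefore what separates primary-endpoint failure from the protocol's Grade 5 to 8 endpoint. The SAP's statement that the two are the same holds only if that row has been left out.

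**3. Size per subject.** The plan gives no power calculation, effect size or event rate (SAP 4), so it has no figure to reproduce. SAP 5 plans about 20 subjects per arm. One reclassified subject moves that arm's responder rate by 1/20 = 5 percentage points.

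**4. Illustration with assumed counts.** The tests are those of the sensitivity analysis in SAP 6.12.1: Wald with null variance, and Barnard's exact test as called in the example code. With 20 per arm and pooled rate p̄,

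z = (p₁ − p₀) / √[p̄(1 − p̄)(1/20 + 1/20)]

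- 18/20 v 12/20: difference 0.30, p̄ = 30/40 = 0.75, SE = √(0.75 × 0.25 × 0.1) = 0.137, z = 2.19. Wald p = 0.028, Barnard p = 0.039. Wald 95% CI for the difference 0.05 to 0.55.
- 17/20 v 12/20 (one VERU-111 responder reclassified): difference 0.25, p̄ = 29/40 = 0.725, SE = √(0.725 × 0.275 × 0.1) = 0.141, z = 1.77. Wald p = 0.077, Barnard p = 0.107. CI −0.02 to 0.52.
- 18/20 v 11/20 (one placebo responder reclassified instead): difference 0.35, p̄ = 0.725, SE = 0.141, z = 2.48. Wald p = 0.013, Barnard p = 0.017.

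With these counts, one reclassification in the VERU-111 arm crosses the two-sided 5% level of SAP 6.12. One in the placebo arm widens the difference. The primary analysis itself is a covariate-adjusted logistic regression, which cannot be reproduced without data.

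**The case against.** The strongest reply is that the affected group is very small. The clause requires that none of the listed measures was started and that resources were the only reason. A patient refused a ventilator but given high-flow oxygen is already Grade 5, and a patient who died before the visit is already a non-responder. What remains is a subject alive at the visit, in diagnosed failure, on no more than mask or prongs, solely for lack of resources. In an unpowered proof-of-concept trial of about 40 subjects, that group may be empty. This stands. It limits the consequence but does not remove the contradiction.

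Four stronger readings are tempting and should not be drawn.

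- *A bias towards VERU-111.* For the individual, the error always turns a failure into a success. The arm that gains is unknown, and nothing in the plan of this double-blind trial makes one arm more likely to gain. The two reclassifications in the illustration move the comparison in opposite directions.
- *A demonstrated change in significance.* The counts are assumed. The choice of test also matters: Fisher's exact test gives p = 0.065 for 18/20 v 12/20 and p = 0.031 for 18/20 v 11/20, which looks like a crossing. Fisher's test is not in the plan, and under the planned sensitivity tests both results are already below 0.05.
- *Lost Grade 5 to 8 results.* The analysis is still done at all three visits, under the primary-endpoint tables. The word redundant in SAP 6.12.2.2 shows that the clause was set aside, and is not a second harm.
- *A ready-made data item.* Protocol 8.4 asks for documentation of care decisions on Days 2 to 21. That is not a diagnosis of respiratory failure at a visit, so it cannot supply the flag alone. SAP section 9 says that all randomized subjects were treated, so a new form item at Days 22 and 29 would largely be retrospective.

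**Conclusion.** The rule contradicts the endpoint printed above it. SAP 6.12.1 states an endpoint with a resource-limitation component and then classifies subjects without it. The Day 15 and Day 22 versions share the gap, and section 9 does not disclose it.

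The size is 5 percentage points in one arm per affected subject, assuming 20 per arm. The number affected is not given and may be zero, and the direction of any effect on the treatment comparison is unknown. The p-values show only that one subject can matter at this sample size, and they rest on assumed counts and unadjusted tests. The documents do not support a claim that the trial's result is biased or that its conclusion would change. They do support correcting or declaring the rule before database lock.

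**What to change.** Before database lock, add this condition to the non-responder definition at Days 15, 22 and 29: *or is clinically diagnosed with respiratory failure at that visit, with none of the listed measures started, solely because of resource limitation*. Make the responder definition its complement.

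Set the flag from existing records: the primary and secondary endpoint assessments that the protocol schedules at Days 15, 22 and 29 (8.5 to 8.7), the resource-limitation documentation of Protocol 8.4, and site queries where these leave doubt. Make the determinations while still blinded to treatment. Report the number of subjects affected by arm and visit, even if it is zero.

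If the records cannot support the flag, declare the omission in SAP section 9 as a change to the primary endpoint and add a sensitivity analysis. One option is to count as non-responders the Grade 3 or 4 subjects who have a resource-limited care decision on record.

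The cost is one sentence, one derivation flag and some record review, with possible site queries. If no subject is affected, the result is unchanged and the report can say so.

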9.3.1 Primary Endpoint

The primary endpoint for the study will be the proportion of subjects that are alive without respiratory failure at Day 29. Respiratory failure is defined endotracheal intubation and mechanical ventilation, extracorporeal membrane oxygenation, high-flow nasal cannula oxygen delivery, noninvasive positive pressure ventilation, clinical diagnosis of respiratory failure with initiation of none of these measures only when clinical decision making is driven solely by resource limitation.

This analysis will compare the percentage of subjects that are alive without respiratory failure on Day 22 (responder). The percentage of subjects that meet these criteria in each of the two treatment groups will be summarized and compared observationally and statistically.

The number and percentage of responders will be summarized by treatment group. Responders will be analyzed using a logistic regression model. This model will include treatment as a factor and study site and WHO Ordinal Scale for Clinical Improvement at baseline as a covariates. Odds ratios, standard errors, 95% confidence intervals and p-values for the treatment difference will be presented.

The primary analysis will be performed on the ITT population. Subjects for whom respiratory failure and/or vital status at Day 29 cannot be established will be excluded from the analysis, noting that the number of such subjects is expected to be minimal. A sensitivity analysis will be performed treating these subjects as non-responders. A further sensitivity analysis also be performed on the mITT population.

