#### **6.12.2** Secondary Endpoints

# 6.12.2.1 Change in mean WHO Ordinal Scale for Clinical Improvement at Day 15, Day 22 and Day 29

The mean change in WHO Ordinal Scale for Clinical Improvement from baseline to Day 15, Day 22 and Day 29 will be assessed.

Baseline for WHO Ordinal Scale is the last available record up to and including Day 1. If subject died or was discharged from the hospital prior to Day 15, 22 or 29 and WHO Ordinal Scale for Clinical Improvement is not collected or record is otherwise missing at those timepoints then the last available observation before or at the time of death/discharge will be carried forward.

Analysis will be performed using two different approaches, including the LOCF values and excluding LOCF values. Further, these analyses will be repeated using separate baseline definition. As the time of WHO Ordinal Scale is collected it cannot be definitely confirmed if Day 1 record was taken before or after start of study treatment. Sensitivity analysis will be performed using the WHO Ordinal Scale from Screening record.

Descriptive statistics (n, mean, standard deviation, median, minimum and maximum) will be summarized for absolute values and change from baseline by treatment group and visit.

Change from baseline will be analyzed using mixed model for repeated measures (MMRM) including treatment, visit and treatment-by-visit interaction as fixed effects, and study site, remdesivir use (No/Yes), dexamethasone use (No/Yes) and WHO Ordinal Scale for Clinical Improvement at baseline as covariates. The resulting F-tests will be based on Kenward-Roger's adjusted degrees of freedom. Subject effect will be assumed to be random and an unstructured covariance structure will be used for within subject variation. If this model does not converge then the following covariance matrices will be used in order until the model converges: Toeplitz, first-order autoregressive, and compound symmetry. Least squares means, standard errors, 95% confidence intervals and p-values for treatments and treatment differences at each visit (study days 15, 22, 29, 45 and 60) will be presented.

QMD Ref: Worldwide-TMP-ST-005-7.0 Effective: 12Aug2019 Governing QMD: Worldwide-SOP-ST-0		
Confidentiality Statement		
This document is the property of Worldwide Clinical Trials Inc. and may not be duplicated, copied, altered or removed from company without		

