# STATISTICAL ANALYSIS PLAN. PHASE 2-3-4

Table Number	Table Title	Included in Preliminary Analysis	Included in DSMB (Table No.)	Validation Method	Shell Number (if repeat)
14.1.5.3	Standard of Care (ITT Population)			IP	
14.2	Efficacy Data				
14.2.1	Primary Efficacy Endpoint				
14.2.1.1	Proportion of Subjects Alive and Free of Respiratory Failure by Visit (ITT Population)	Yes		IP	
14.2.1.2	Logistic Regression for Proportion of Subjects Alive and Free of Respiratory Failure by Visit (ITT Population)	Yes		Stat IP	
14.2.1.2a	Responder Rates for Proportion of Subjects Alive and Free of Respiratory Failure by Visit (ITT Population)			Stat IP	
14.2.1.3	Proportion of Subjects Alive and Free of Respiratory Failure by Visit (EE Population)			IP	14.2.1.1
14.2.1.4	Logistic Regression for Proportion of Subjects Alive and Free of Respiratory Failure by Visit (EE Population)			Stat IP	14.2.1.2
14.2.2- 14.2.11	Secondary Efficacy Endpoints				
14.2.2.1	Descriptive Statistics for WHO Ordinal Scale for Clinical Improvement by Visit - With LOCF values (ITT Population)	Yes		IP	
14.2.2.2	Mixed Model for Repeated Measures (MMRM) for Change from Baseline in WHO Ordinal Scale for Clinical Improvement - With LOCF values (ITT Population)	Yes		Stat IP	
14.2.2.3	Descriptive Statistics for WHO Ordinal Scale for Clinical Improvement by Visit - Without LOCF values (ITT Population)			IP	14.2.2.1
14.2.2.4	Mixed Model for Repeated Measures (MMRM) for Change from Baseline in WHO Ordinal Scale for Clinical Improvement - Without LOCF values (ITT Population)			Stat IP	14.2.2.2
14.2.2.5	Descriptive Statistics for WHO Ordinal Scale for Clinical Improvement by Visit - With LOCF values - Screening as Baseline (ITT Population)	Yes		IP	14.2.2.1
14.2.2.6	Mixed Model for Repeated Measures (MMRM) for Change from Baseline in WHO Ordinal Scale for Clinical Improvement - With LOCF values - Screening as Baseline (ITT Population)	Yes		Stat IP	14.2.2.2
14.2.2.7	Descriptive Statistics for WHO Ordinal Scale for Clinical Improvement by Visit - Without LOCF values - Screening as Baseline (ITT Population)			IP	14.2.2.1
14.2.2.8	Mixed Model for Repeated Measures (MMRM) for Change from Baseline in WHO Ordinal Scale for Clinical Improvement - Without LOCF values - Screening as Baseline (ITT Population)			Stat IP	14.2.2.2
14.2.2.9	Area Under Curve of WHO Ordinal Scale for Clinical Improvement (ITT Population)			IP	

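### SAP 6.12.1 substitutes a discharge carry-forward for the protocol's missing-status rule, drops the non-responder sensitivity analysis undeclared, and cannot count resource-limited respiratory failure

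*SAP*

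**What the plan says.** Protocol 9.3.1 has a two-part rule. For the primary analysis, "Subjects for whom respiratory failure and/or vital status at Day 29 cannot be established will be excluded from the analysis"; the protocol expects few such subjects. Then "A sensitivity analysis will be performed treating these subjects as non-responders". A further sensitivity analysis uses the mITT population.

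SAP 6.12.1 classifies by WHO grade. "Responders are subjects who have Grade 0-4 on the WHO Ordinal Scale for Clinical Improvement on Day 29". "Non-responders are subjects who died before Day 29 or has Grade 5, 6, 7, or 8 on the WHO Ordinal Scale". If a subject was discharged before Day 29 and the score "is not collected at Day 29 then the last available observation before or at the time of discharge will be carried forward". The section has no exclusion rule. Its sensitivity analyses are a repeat on the Efficacy Evaluable population and a comparison of responder rates by the Wald method.

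The definition of respiratory failure at the head of the same section ends with "clinical diagnosis of respiratory failure with initiation of none of these measures only when clinical decision making is driven solely by resource limitation".

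For the change in WHO score (SAP 6.12.2.1) the plan is different: "Analysis will be performed using two different approaches, including the LOCF values and excluding LOCF values".

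SAP Section 9 lists these departures from the protocol: added covariates, the dropped Grade 5-8 endpoint, no interim analysis, the revised ITT definition and the new EE population.

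**The concern.** There are two separate problems in one section.

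First, status at discharge stands in for status at Day 29. A subject who is readmitted with respiratory failure and has no Day 29 score is counted as a responder. Read literally, the rule also passes over any score taken after discharge, such as at the scheduled Day 22 visit. The protocol had planned a check on exactly this kind of subject. The SAP removes it and does not say so, so the primary result would rest on an undeclared imputation with no analysis of how far it depends on it.

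Second, the responder rule does not implement the definition above it. A limb of the endpoint that is written out in full can never be counted for a living subject.

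The stakes go beyond one table. SAP 6.12.2.6 repeats the primary method at Days 15 and 22, and the protocol summary ties the decision on Phase 3 to the Day 22 version of this endpoint.

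**Working it through.** **Missing-status rule, side by side**

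| Subject with no Day 29 score | Protocol 9.3.1, if status cannot be established | SAP 6.12.1 |
|---|---|---|
| Known death before Day 29 | Not applicable: status is known | Non-responder |
| Discharged, last score at or before discharge 0-4 | Excluded; non-responder in sensitivity analysis | Responder |
| Discharged, last such score 5-7 | Excluded; non-responder in sensitivity analysis | Non-responder |
| Alive, not discharged | Excluded; non-responder in sensitivity analysis | No rule |

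The planned outputs for the primary endpoint (SAP Section 11) are tables 14.2.1.1, 14.2.1.2, 14.2.1.2a, 14.2.1.3 and 14.2.1.4. They cover the ITT and EE populations. None varies the missing-data rule, and none uses mITT. Section 9 mentions neither the carry-forward nor the lost analyses. The LOCF note in the SAP's amendment table concerns 6.12.2.1, not 6.12.1.

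**Resource-limited failure**

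In SAP 3.2, Grade 5 is non-invasive ventilation or high-flow oxygen, Grade 6 is intubation and mechanical ventilation, and Grade 7 adds organ support. All three describe support in use. A living subject diagnosed with respiratory failure but given none of these for lack of resources therefore scores 4 or lower. The definition calls that subject a failure; the Grade 0-4 rule calls the same subject a responder.

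**Size**

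The documents give no power, effect size or expected responder rate, so there is no figure to reproduce. From the documents: 20 per arm (SAP Section 5), two-sided 5% level (SAP 6.12), and a risk-difference test with null variance (the PROC FREQ code in 6.12.1). All counts below are assumed.

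With a and b responders out of n1 and n2, d = a/n1 - b/n2, pooled p = (a+b)/(n1+n2), z = d / sqrt[p(1-p)(1/n1+1/n2)].

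SAP rule, 19/20 against 14/20: p = 33/40 = 0.825; z = 0.25 / sqrt(0.825 x 0.175 x 0.1) = 0.25/0.1202 = 2.08; two-sided p=0.038.

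Now let one of those counted responders have unestablished status:

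| Unestablished subject | Excluded | As non-responder |
|---|---|---|
| One of the 19 | 18/19 v 14/20: 24.7 points, p=0.044 | 18/20 v 14/20: 20 points, p=0.11 |
| One of the 14 | 19/20 v 13/19: 26.6 points, p=0.031 | 19/20 v 13/20: 30 points, p=0.018 |
| One in each arm | 18/19 v 13/19: 26.3 points, p=0.036 | 18/20 v 13/20: 25 points, p=0.058 |

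Barnard's exact test, also requested in the SAP code, gives 0.049 for 19/20 v 14/20, 0.053 for 18/19 v 14/20, 0.154 for 18/20 v 14/20 and 0.022 for 19/20 v 13/20.

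A larger imbalance, again assumed, with 18/20 v 13/20 under the SAP rule (25 points, p=0.058):

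- Three unestablished on VERU-111, none on placebo: excluded, 15/17 v 13/20, 23.2 points, p=0.101; as non-responders, 15/20 v 13/20, 10 points, p=0.490.
- Three on placebo, none on VERU-111: excluded, 18/20 v 10/17, 31.2 points, p=0.028; as non-responders, 18/20 v 10/20, 40 points, p=0.006.

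**The case against.** The best case for the SAP has five parts.

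- **The carry-forward is narrow.** It reaches only discharged subjects with no Day 29 score, known deaths stay non-responders, and the protocol leaves analysis detail to the SAP. This is correct. A living, undischarged subject without a score would probably drop out of the logistic model, much as under exclusion. But the SAP does not say so, and leaving detail to the SAP does not excuse omitting a named sensitivity analysis without listing it.
- **Against the protocol's primary rule, exclusion, little moves.** In the one-subject scenarios the estimate is 24.7 to 26.6 points instead of 25, and every Wald p-value stays below 0.05. That stands, although Barnard's test goes from 0.049 to 0.053 in one of them. The 5-point shifts come from the non-responder analysis, which is the one removed. The starting counts were also chosen near the 5% boundary, and the test is the supportive one, not the logistic model.
- **Dependence on the rule could be pieced together.** Tables 14.2.2.1 and 14.2.2.3 show WHO scores with and without LOCF, and listings 16.2.6.1 and 16.2.6.2 give individual data. These indicate how many scores were carried, but they do not re-analyse the primary endpoint.
- **The grade-based responder rule is disclosed in 6.12.2.2.** It is, but without noting that it loses a limb of the definition.
- **No readmitted or resource-limited case is indicated, and the trial is an unpowered proof of concept.** True. This limits the likely size, not the inconsistency.

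**Conclusion.** The point holds on the text. For discharged subjects the SAP replaces the protocol's exclusion with a carry-forward; for undischarged subjects it leaves no rule; it drops the non-responder sensitivity analysis (and the mITT one); and it declares none of this in Section 9. Separately, the Grade 0-4 rule contradicts the definition of respiratory failure in its own section.

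One subject of 20 is 5 points in an arm, and on assumed counts one subject can move the treatment difference by 5 points either way. How many subjects are affected is unknown, may be none, and is expected by the protocol to be minimal. The direction of any bias is not established, because it depends on which arm those subjects are in. This should be corrected. It does not by itself show that the primary result would be wrong.

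**What to change.** 1. Before any carry-forward, set the Day 29 status of discharged subjects from information already scheduled: the Day 22 and Day 29 assessments, the Day 45 and Day 60 contacts, and SAE reports of death or rehospitalization (Protocol 8.6 to 8.8 and 8.11.3). Write the rule down first and apply it without sight of treatment assignment. State what happens to an undischarged subject with no Day 29 score.
2. Restore the sensitivity analysis that counts unestablished Day 29 status as non-response, and also show the protocol's exclusion analysis.
3. Extend the non-responder definition to a documented clinical diagnosis of respiratory failure left untreated solely because of resource limitation. The sources are the Protocol 8.4 notes on resource-limited care decisions and whatever the Day 22 and Day 29 treatment records show. Those notes are specified only for Days 2-21, so the SAP should state that this limb may be incomplete at Day 29.
4. List the carry-forward and every added or dropped analysis of the primary endpoint, mITT included, in SAP Section 9.

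The cost is SAP wording and one or two tables; the post-discharge contacts and SAE reports are already collected. The reported responder rate may become slightly less favourable.
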